The goal of this project is to obtain proof the rehabilitation technique has the potential to be successfully translated to humans. To achieve this goal, we will recruit a sample size of 10 hemianopia subjects in this study in hopes of having at least 5 participants complete all study sessions. This study is exploratory; the findings from this study will be used to design future studies. The observed treatment response pattern will be reported, and those data used for informed estimates of incidence for future research. Prior animal model studies demonstrated a high success rate in the rehabilitation strategy, with 100% of 11 hemianopic cats regaining visual field. Assuming that 80% of subjects will have a successful result, using n=5 subjects will allow for estimation of a 95% confidence interval with width 0.35 units either side of the estimate [22].

Interventions and Interactions

Interventions

Cross-Modal Visual Auditory Rehabilitation - Cross-modal visual auditory rehabilitation is based on the rehabilitation paradigm derived from previous animal model studies. The rehabilitation will be carried out using a virtual reality rehabilitation (VR) system. The rehabilitation system uses a customized commercial wireless VR headset, the Samsung Gear VR, to run custom-made rehabilitation software.

The cross-modal rehabilitation software provides a gray colored, neutral environment for patients, with minimal distractions from rehabilitation. Subjects will be asked to fixate on a colored fixation spot in the center of the visual field for 1 second before being randomly presented with either a visual stimulus in the normal intact visual field or a spatiotemporally coincident audio-visual stimulus in the hemianopic side. Auditory-visual stimulus and visual stimulus will be presented at a ratio of 9:1 respectively. The design of the fixed, predictable timing and 9:1 ratio will help subjects shift their attention to the blind field.

[figure not shown]

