Auditory stimulus consists of a brief burst of white noise, lasting approximately 100 ms. Visual stimulus is a white colored orb positioned against the dark, neutral background and will be displayed for 1-2 seconds. The longer duration of the visual stimulus will serve to provide stimulus location feedback for patients. Patients will be instructed to orient their eyes and head toward stimuli in the hemianopic field and to push a button on a controller upon detecting stimuli. This part of the task will serve to boost motivation and maintain attention during training. The software will also record these responses and reaction times, based on the button presses, and store this data for later review. The next trial will begin 3-4 seconds after the visual or auditory-visual stimulus disappears and when the patient re-fixates on the fixation point.

Cross-modal visual auditory rehabilitation consists of a total of 200 trials / day (about 30 min) over 1 month. Given the results from animal model studies, we expect progress to be observable after 2-3 weeks of cross-modal rehabilitation, and completion of rehabilitation 1 month after the start of cross-modal training.

While we expect most patients will perform rehabilitation using the virtual reality rehabilitation system, patients may also complete rehabilitation with a free-field frame device if they are not comfortable with using a VR headset. The free-field frame device uses a semi-circular frame to hold LED lights (visual stimulus) and speakers (auditory stimulus) in front of the patient. These lights and speakers can be used to deliver the same cross-modal visual auditory rehabilitation paradigm. The device is also used to perform peripheral visual field tests, and is described in more detail below in *peripheral visual field test*.

Tests

Humphrey Visual Field (HVF) Test - The HVF test is a common test given to map the visual field. During the HVF test, light is projected into a white bowl with a standardized background light intensity to form a circular stimulus, around 30 cm away from the patient's eye. The overall field mapping technique used is a form of static perimetry, where a stimulus appears in various areas of the field of vision. The patient indicates when they can see the stimulus and the perimetrist then records the point where the stimulus was seen. These datapoints are used to determine the patient's visual field.

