Peripheral Visual Field Test - Since the Humphrey visual field test only measures up to 30° in the periphery, an additional peripheral visual field test will be administered using a semi-circular frame device (fig. 1) set 50 cm in front of the subject with LED lights acting as visual stimulus, located at azimuths of 15°, 30°, 45°, 60°, and 75°, as well as a center fixation light. Lights will be presented at a random time with a fixation period between each trial and locations selected randomly. Subjects will be asked to fixate on the center fixation light while lights are presented at random locations at random times (0-1.5 seconds). Upon detecting a light, subjects will press a button. Subject responses will be used to determine how far in the periphery, up to 75°, a subject can see. The test will present a total of 5 trials at each location in both the intact and hemianopic side, as well as 5 trials with no stimuli.

This test uses the free-field frame device to position visual and auditory stimuli, in the form of LED lights and speakers, at different angles of the patient. The patient is asked to maintain visual fixation on a lit LED light straight ahead during the test. Speakers will play a brief burst of white noise from a random location 15° or 45° on either the left or right side. The subject will be asked to identify where the sound is originating from either verbally or using a button response pad. During this test, subjects' eyes may be videotaped or photographed. These recordings or photos will be reviewed by a member of the study team to confirm the subject is able to properly maintain visual fixation.

Figure 1: Free-field frame device

track rehabilitation progress. The test consists of 30 trials with visual stimulus presented either 15°, 30°, 45° in either the hemianopia field or the intact field at random time intervals.

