The virtual reality headset and headphones will provide visual and auditory stimulation used in the rehabilitation training. Each rehabilitation session will consist of 200 trials. At the end of each rehabilitation session, subjects will perform a brief 2-minute VR visual field progress test with the VR system to track rehabilitation progress. The rehabilitation will be considered complete once patients can reliably detect stimuli 45° in the hemianopic field.

If patients cannot detect stimuli at 15° by the end of 30 days of rehabilitation, they will repeat the rehabilitation for one more month, in order to determine if the slow progress or lack of progress is caused by simply not spending enough time performing rehabilitation.

Study Session 63: Post Rehabilitation Tests - Subject visual field did not increase (1 hour)

If no visual field improvement (measured by virtual reality visual field progress tests) has occurred at the end of the 2nd round of rehabilitation, subjects will complete one last visit, where they will be given the

NEI VFQ-25 and VA LV VFQ-48 questionnaires to complete. This visit will occur on the Wake Forest Baptist Medical Center campus.

Study Session 33: Post Rehabilitation Tests - Subject visual field increase (1.5 hours)

If a subject shows visual field expansion in the virtual reality visual field progress test, subjects will be given a **Peripheral Visual Field Test, NEI VFQ-25 and VA LV VFQ-48 Questionnaires** in order to measure visual field expansion and improvements in quality of life.

In previous animal studies, rehabilitated hemianopic animals could only detect spatial frequencies of 2 cycles/degree compared to over 5 cycles/degree in the (normal) intact animals. We hypothesize the subcortical visual pathway mediating the restored visual functions may not have the same capabilities as the visual cortex it is replacing. Therefore, recovered vision may have lower visual acuity. The different pathways involved in cross-modal rehabilitation may also affect abilities for shape recognition in the newly recovered visual field. We will explore whether this is the case with a simple **shape recognition test, visual acuity test, and color vision test** during this visit. Subjects will complete this visit on the Wake Forest Baptist Medical Center campus.

Study Session 34: Humphrey Visual Field Post-Intervention Test (1 hour)

Subjects will report to an optometrist for a **Humphrey Visual Field** perimetry test.

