Study Session 35: 3 Month Post-Intervention Follow-up Tests (1 hour)

Subjects will complete a follow-up visit 3 months after the end of rehabilitation on the Wake Forest Baptist Medical Center campus. The follow-up visit will consist of a peripheral visual field test, and NEI VFQ-25 and VA LV VFQ-48 questionnaires.

Study Session 36: 6 Month Post-Intervention Follow-up Tests (1 hour)

Subjects will complete a final follow-up visit 6 months after the end of rehabilitation on the Wake Forest Baptist Medical Center campus. The follow-up visit will consist of a peripheral visual field test, and NEI VFQ-25 and VA LV VFQ-48 questionnaires.

Outcome Measure(s)

The primary outcomes for all participants will be the visual field measurements from Humphrey Visual Field and peripheral frame test, with comparisons made before (visits 1 and 2) and after treatment (visits 34 and 35 or visits 63 and 64).

Secondary outcome measures will include differences in quality of life questionnaire results from before (visit 1) and after treatment (visit 33 or 63) and changes in VR progress test results during the course of rehabilitation (visits 3-32 and 33-62 if a subject repeats rehabilitation).

Exploratory outcome measures will be collected in subjects with restored visual fields. The qualities of recovered visual field will be examined with visual acuity, color recognition, and shape recognition tests after rehabilitation (visit 33 or 63).

Analytical Plan

Results will be analyzed initially using descriptive statistics. The improvement of visual detections will be assessed by using a two-way ANOVA on the percentages of visual detections to stimuli presented in the hemianopic hemifield in the peripheral visual field tests before and after rehabilitation. Comparisons for subjects will be done using chi square tests for proportions, and t-tests or ANOVA procedures for continuous variables. Other inferential statistical analysis will be conducted as appropriate.

Human Subjects Protection

Subject Recruitment Methods

Protocol version: 2

Protocol updated 7.01.20

Subjects with homonymous hemianopia on either the left and right side of the visual field will be recruited using resources from Wake Forest University Health Sciences' Clinical and Translational Science Institute (CTSI). Members of the PI's research team will perform recruitment. Coordination of potential participants' visit will be done by phone or in person conversation or by email.

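### The primary field results pool one-month and two-month training, and subjects who repeat have no primary field test after the first month

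*Combined protocol and SAP*

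**What the plan says.** The Interventions section sets 200 trials a day over 1 month and expects "completion of rehabilitation 1 month after the start of cross-modal training". Study Sessions 3–32 are those 30 daily sessions. For subjects who have not progressed, the rule is "If patients cannot detect stimuli at 15° by the end of 30 days of rehabilitation, they will repeat the rehabilitation for one more month", and its purpose is given as "in order to determine if the slow progress or lack of progress is caused by simply not spending enough time performing rehabilitation".

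Outcome Measure(s) states: "The primary outcomes for all participants will be the visual field measurements from Humphrey Visual Field and peripheral frame test". The before value comes from visits 1 and 2. The later value is taken "after treatment (visits 34 and 35 or visits 63 and 64". Changes in the VR progress test over visits 3–32, and over 33–62 for repeaters, are a secondary outcome.

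The schedule makes the Session 33 frame test conditional on expansion in the VR progress test. Session 34 is the Humphrey test, and Session 35 is the 3-month follow-up. Session 63, for repeaters with no VR improvement, lists the two questionnaires and no field test. No Session 64 is described.

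On the VR test, the training section says "At the end of each rehabilitation session, subjects will perform a brief 2-minute VR visual field progress test with the VR system", and the test description says "The test consists of 30 trials with visual stimulus presented either 15°, 30°, 45° in either the hemianopia field or the intact field".

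The Analytical Plan names a two-way ANOVA on hemianopic-side detection percentages in the frame test, before and after. It does not name the factors and states no term for training duration. The Sample Size section says what the results are for: "The observed treatment response pattern will be reported, and those data used for informed estimates of incidence for future research".

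**The concern.** The second month is assigned by poor response at day 30, and the primary comparison then uses the later result. The after value is therefore not tied to one amount of training, and the subjects with the most training are those who did worst at one month. Two uses of the data suffer.

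First, whoever designs the next study needs to know whether a response rate follows one month of training or up to two. A single pooled rate does not say.

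Second, the plan wants to learn whether more training time helps slow responders. On the primary tests, a repeater has a baseline value and at best a value after round 2. The gain in month 1 and the gain in month 2 cannot be told apart. A repeater who never improves has no post-training primary field value described at all, although the primary outcome is said to cover all participants.

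**Working it through.** **1. Who is scheduled for a primary field test, and when**

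| Subject | End of round 1 | End of round 2 |
|---|---|---|
| VR expansion in round 1 | Frame (Session 33), Humphrey (Session 34) | not applicable |
| Repeater, improves in round 2 | none scheduled | implied by visits 63 and 64; content not described |
| Repeater, no improvement | none scheduled | none listed (Session 63: questionnaires only) |

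The VR progress test covers the end of round 1 in all three rows for those who train on VR.

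**2. Visit numbers.** Read literally, visits 34 and 35 put the one-round subjects' frame result at the 3-month follow-up, while visit 63 puts the repeaters' at the end of training. The secondary outcomes use visit 33 or 63, which suggests that 33 and 34 were meant as the counterpart of 63 and 64. The two sections need to be reconciled either way.

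**3. Training received.** If k of 5 completers repeat, mean planned sessions are (30 × (5 − k) + 60k) / 5 = 30 + 6k, so from 30 to 60. The 30 is itself approximate: training counts as complete at reliable detection at 45°, and a restart resets the day count.

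**4. The plan's own figure.** With n = 5 and assumed success 0.80, the 95% half-width is 1.96 × √(0.80 × 0.20 / 5) = 0.3506, which reproduces the stated 0.35. The Sample Size section does not say whether the 80% is a rate after one round or after up to two.

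**5. How far the two rates can differ.** Let p1 be the success rate after round 1 and q the success rate in round 2 among repeaters. The documents give neither, so all values are assumed, and failure at round 1 is taken to mean repeating.

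Rate after up to two rounds = p1 + (1 − p1) × q. Gap = (1 − p1) × q.

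| p1 | q | Rate after up to two rounds | Gap (points) |
|---|---|---|---|
| 0.60 | 0 | 0.60 | 0 |
| 0.60 | 0.25 | 0.60 + 0.40 × 0.25 = 0.70 | 10 |
| 0.60 | 0.50 | 0.60 + 0.40 × 0.50 = 0.80 | 20 |
| 0.80 | 0.20 | 0.80 + 0.20 × 0.20 = 0.84 | 4 |
| 0.80 | 0.80 | 0.80 + 0.20 × 0.80 = 0.96 | 16 |
| 0.50 | 0.50 | 0.50 + 0.50 × 0.50 = 0.75 | 25 |

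For p1 from 0.2 to 0.8 and q no larger than p1, the gap runs from 0 to 25 points.

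**6. How likely mixing is.** With 5 independent completers and a 20% chance of failing at day 30, the chance of at least one repeater is 1 − 0.8⁵ = 0.67. If both rounds succeed at the same rate and the final rate is 80%, then p1 = 1 − √0.2 = 0.553, and the chance is 1 − 0.553⁵ = 0.95. One responder among 5 is 1/5 = 20 points.

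**7. Size of the added test.** Frame test: 5 azimuths × 2 sides × 5 trials = 50, plus 5 no-stimulus trials = 55.

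**The case against.** The strongest reply is that the plan already measures the field at day 30 and openly provides for the repeat. Much of this stands, and it rules out several stronger readings.

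- A reader might infer that no field test is taken at a common time. That is not so. The VR test follows every session, at 15°, 30° and 45° on both sides.
- A reader might infer that only the final result is used. That is true of the primary outcome only; the secondary VR outcome spans both rounds.
- A reader might infer that the one-month response rate is lost. By the protocol's own 15° criterion it is not: count who repeated. What is lost is the day-30 value on the frame and Humphrey tests.
- A reader might infer that day 30 has to be the primary time for everyone. An end-of-training result is a legitimate choice in an exploratory study that hopes for 5 completers.
- A reader might take 60% against 80% as the expected distortion. Those inputs are assumed, and the gap can be zero. They also concern a response rate, whereas the stated ANOVA is on detection percentages.

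The reply does not make the VR test a full substitute. It stops at 45°, against 75° for the frame. It appears to be the measure that decides who repeats, so part of any later VR gain may be regression to the mean. Its length is given as 5 minutes in one place and 2 in another. Subjects may train on the free-field frame instead, and no per-session progress test is described for that device.

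**Conclusion.** The point holds as a gap in the definition and reporting of the primary outcome, not as a calculation error. The primary after values pool about 30-session and about 60-session results, with the extra training selected by poor response. Repeaters have no primary field test between rounds, and those who do not improve have none listed afterwards. These statements rest on the text alone.

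The size rests on assumptions: 0 to 25 percentage points between the one-round rate and the rate after up to two rounds, for p1 from 0.2 to 0.8 and q no larger than p1. With 5 completers, a single second-round responder accounts for 20 points. The documents do not support saying that the reported rate will be inflated by a known amount, or that one-month response cannot be recovered in any form.

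**What to change.** 1. Give repeaters the existing 55-trial frame test at the end of the first round, before the second starts, and again at Session 63 whatever the VR result.
2. Report frame results and response rates separately after round 1 and at end of training, by number of rounds and with actual session counts. State how repeaters enter the ANOVA. The end-of-training comparison may stay primary if it is labelled as the result after up to two rounds.
3. Reconcile the visit numbers in Outcome Measure(s) (34 and 35, 63 and 64) with the schedule, where the post-training frame test is at Session 33, Session 35 is the 3-month follow-up and Session 64 is not described.

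The cost is one or two short extra tests on existing equipment for repeaters only, a possible campus trip for those training at home, one or two more exposures to the test, and a one-month rate that may be lower than the final one. The second round itself is unchanged. Two limits remain: Humphrey would still have no value between rounds, and without a control group the frame results show change over the added month, not its cause.

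### The visit schedule leaves subjects with no VR improvement without the post-treatment primary tests that Outcome Measure(s) requires of everyone

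*Combined protocol and SAP*

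**What the plan says.** All references are to the combined protocol and SAP.

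- **Outcome Measure(s):** "The primary outcomes for all participants will be the visual field measurements from Humphrey Visual Field and peripheral frame test". The post-treatment visits named are 34 and 35, or 63 and 64.
- **Analytical Plan:** improvement is assessed by a two-way ANOVA of detection percentages in the hemianopic hemifield on the frame test, before and after rehabilitation.
- **Study Sessions 3–32:** "If patients cannot detect stimuli at 15° by the end of 30 days of rehabilitation, they will repeat the rehabilitation for one more month".
- **Study Session 33** (field increased): "If a subject shows visual field expansion in the virtual reality visual field progress test, subjects will be given a" frame test and both questionnaires, plus the exploratory acuity, colour and shape tests.
- **Study Session 34:** Humphrey test. **Sessions 35 and 36:** 3-month and 6-month follow-up, each with the frame test and both questionnaires. None of these three states a condition of its own.
- **Study Session 63** (field did not increase, 1 hour): if the VR progress test shows no improvement, "at the end of the 2nd round of rehabilitation, subjects will complete one last visit, where they will be given the". That sentence ends by naming only the two quality-of-life instruments. No field test is listed.

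The available text describes no Session 64. Figure 2, the study timeline, is not reproduced in that text and may list one.

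**The concern.** One section promises the primary measurements on everybody. The other makes the frame test conditional on a related field result and ends participation with questionnaires for those who fail it. Staff cannot follow both. If they follow the visit schedule, the post-treatment primary outcome is missing precisely because the subject did not respond.

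The Design section compares subjects with their own pre-intervention measures, so there is no control arm to absorb that selection. The ANOVA would compare before with after only in subjects who passed a related test, and the estimate for Specific Aim 1 would tend to be too high. Sample Size says the findings will inform later studies, so an inflated change would carry forward. Measurements not taken at the end of rehabilitation cannot be recovered afterwards.

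**Working it through.** **1. Which subject gets which post-treatment primary test**

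| Subject | Frame test | Humphrey test |
|---|---|---|
| VR expansion in round 1 | Session 33 | Session 34 |
| VR expansion only in round 2 | Not described; Outcome Measure(s) implies visits 63 and 64 | Same |
| No VR improvement after round 2 | None listed (Session 63, questionnaires only) | None listed |
| Detects 15° at day 30 but shows no expansion | Meets neither branch | Unclear |
| Trained on the free-field frame, not VR | No gate test named | Unclear |

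That non-improvers also miss Sessions 34 to 36 is an inference: Session 63 is described as their final visit, and Outcome Measure(s) treats visits 33–62 as training sessions for a subject who repeats. The last two rows are gaps of unknown size, and the conclusion does not rest on them.

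**2. Visit numbers**

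Session 34 is the Humphrey test and Session 35 is the 3-month follow-up. The frame test straight after treatment is Session 33. The two pairs also disagree with each other: a second round adds 30 sessions, and 34 + 30 = 64, 35 + 30 = 65. The pair 63 and 64 corresponds to 33 and 34.

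Outcome Measure(s) also puts the exploratory tests in restored fields at visit 33 or 63. Visit 63 therefore serves second-round improvers as well, with different content from the Session 63 described.

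**3. Inputs from Sample Size**

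80% assumed success; 10 recruited, at least 5 completers hoped for. The plan's own figure reproduces: 1.96 × √(0.8 × 0.2 / 5) = 0.3506, stated as 0.35. Success is not defined there. Below, p is the share showing VR expansion, and p = 0.8 is an assumption.

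**4. Chance that at least one subject lacks the primary tests: 1 − pⁿ**

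| p | n = 5 | n = 10 |
|---|---|---|
| 0.95 | 0.226 | 0.401 |
| 0.90 | 0.410 | 0.651 |
| 0.80 | 0.672 | 0.893 |
| 0.50 | 0.969 | 0.999 |

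Expected number untested at p = 0.8: 0.2 × 5 = 1, or 0.2 × 10 = 2.

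**5. Overstatement if there is a true effect**

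Let untested subjects change by a fraction f of the improvers' mean change, and let the VR gate sort subjects perfectly. Then tested mean / all-participant mean = 1 / (p + (1 − p)f).

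- f = 0: 1.05 (p = 0.95), 1.11 (0.90), 1.25 (0.80), 2.0 (0.50).
- p = 0.80: 1/(0.8 + 0.2 × 0.25) = 1.18 at f = 0.25; 1/(0.8 + 0.2 × 0.5) = 1.11 at f = 0.5.

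**6. Bias if there is no true effect**

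Assume VR and frame changes are bivariate normal with correlation r, and only the top share g on VR is tested. The bias in SD units of frame change is r × φ(z)/g, with z the (1 − g) normal quantile. φ(z)/g is 0.350, 0.798 and 1.400 for g = 0.8, 0.5 and 0.2.

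| g | r = 0.3 | r = 0.7 |
|---|---|---|
| 0.8 | 0.10 | 0.24 |
| 0.5 | 0.24 | 0.56 |
| 0.2 | 0.42 | 0.98 |

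At r = 0 the bias is 0. The documents give neither r, g nor the SD, so no single figure can be chosen.

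**7. Can VR data stand in?**

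Not fully. The VR progress test covers 15°, 30° and 45°; the frame test adds 60° and 75°, two of its five positions per side.

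**The case against.** The strongest reply is that this is a drafting slip and nobody intends to leave non-improvers untested. Outcome Measure(s) covers all participants and names a pair of visits after a second round. Session 63 is allotted 1 hour, the same as Sessions 35 and 36, which fit the frame test and both questionnaires. Figure 2 may show a Session 64 with field testing. This reading may be right, but it does not repair the text: the Session 63 description would still direct staff to give questionnaires only, and visits 63 and 64 could equally be meant only for second-round improvers.

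Second, the sizes are illustrations. If success requires more than some VR expansion, the share with expansion exceeds 80% and the 90–95% rows apply (23% to 41% at n = 5). The ratios assume a perfect gate. The null-bias figures assume normality for a percentage based on 5 trials per location, where a floor in the blind field is plausible; a small SD would make the bias few percentage points. The 20% pass share has no source in the documents. All of this stands, and the contradiction does not depend on these figures.

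Third, the study is exploratory, and its one stated precision target is a response proportion. That proportion is not affected, because non-improvers can still be counted as failures. VR progress results are also kept as a secondary outcome. This limits the harm to the before/after field comparison, but that comparison is the primary outcome.

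Finally, different content at visit 63 for improvers and non-improvers is not contradictory in itself. It only needs to be written down.

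**Conclusion.** The concern holds and must be fixed. The conflict between Outcome Measure(s) and the Session 33 and 63 descriptions is plain on the text, and so are the mismatched post-treatment visit numbers. Confidence in both is high.

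The actual bias is uncertain in size. It arises only if the visit schedule is followed, and the subjects who would show its size are those not tested. If 80% show VR expansion, about 1 of 5 or 2 of 10 subjects would lack the primary tests. The mean change would be overstated by a factor of 1.11 to 1.25 if non-improvers change by between half of the improvers' change and nothing, with a perfect gate.

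**What to change.** Reconcile the visit descriptions, Outcome Measure(s) and Figure 2 as follows, with the sponsor confirming the intended numbering.

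- Give every subject the frame test and the Humphrey test at the end of rehabilitation whatever the VR result, including second-round improvers, subjects who meet neither branch, and those trained on the free-field frame.
- Add the frame test to Session 63 and define Session 64 as the Humphrey test.
- Correct the post-treatment visits to 33 and 34, or 63 and 64.
- State that second-round improvers have the Session 33 tests at Session 63, and whether Sessions 35 and 36 apply to non-improvers.
- Keep the VR condition only for the exploratory acuity, colour and shape tests.
- In the Analytical Plan, include all subjects with post-treatment data in the primary comparison and report how many lack it.

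The cost is protocol wording and, for each non-improver, one short frame test within a visit already allotted 1 hour and one 1-hour optometry visit. The downside is that extra visit for people who saw no benefit. Outcome Measure(s) already requires both tests of them.

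### Subjects with no VR improvement after two rounds get no post-treatment field test, although the primary outcome is set for all participants

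*Combined protocol and SAP*

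**What the plan says.** All references are to the combined protocol and SAP.

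- **Outcome Measure(s):** "The primary outcomes for all participants will be the visual field measurements from Humphrey Visual Field and peripheral frame test". The comparison is between visits 1 and 2 and the values "after treatment (visits 34 and 35 or visits 63 and 64".
- **Analytical Plan:** the two-way ANOVA uses the percentage of stimuli detected in the hemianopic field "in the peripheral visual field tests before and after rehabilitation".
- **Study Sessions 3 – 32:** "If patients cannot detect stimuli at 15° by the end of 30 days of rehabilitation, they will repeat the rehabilitation for one more month".
- **Study Session 63** (no visual field increase): "at the end of the 2nd round of rehabilitation, subjects will complete one last visit, where they will be given the" two quality-of-life questionnaires, which are the NEI VFQ-25 and the VA LV VFQ-48. The visit is on campus and is allotted 1 hour. No field test is listed.
- **Study Session 33** (frame test, questionnaires and recovered-vision tests): applies "If a subject shows visual field expansion in the virtual reality visual field progress test".
- **Study Sessions 34 to 36:** Humphrey test, then the 3-month and 6-month follow-ups with the frame test. None states a responder condition.
- **Session 64:** named in Outcome Measure(s) but described nowhere in the text.

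**The concern.** The outcome section promises primary data on everyone, but the visit schedule does not collect them from one group: subjects who trained for two months without VR improvement. The missing values would not be accidental. The schedule creates them, and it does so on the result of a test closely related to the primary one. No missing-data rule is given.

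A before/after comparison on the available frame tests would then leave out the subjects least likely to have gained. The pre/post contrast is the only efficacy comparison in this single-group study, so the size of the mean change on the primary measure is at stake. The VR progress test cannot stand in for it. It is a secondary outcome and presents stimuli at 15°, 30° and 45° only, whereas the frame test also covers 60° and 75°.

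**Working it through.** **1. Can the text be read so that a two-round non-responder has a post-treatment field test?**

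- *Session 63 itself.* It lists questionnaires only. It is on campus, and the Setting section places Humphrey testing at an optometrist's office.
- *Sessions 34 to 36.* They carry no responder condition, but Session 63 is the last visit for this subject.
- *Visits 63 and 64 as meant for repeaters who gained.* The outcome section puts the recovered-field tests, including the "shape recognition tests after rehabilitation (visit 33 or 63"), in subjects with restored fields, which fits this reading. The non-responder still has no field test.
- *Visits 63 and 64 as meant for all repeaters.* Field tests are then intended, but Session 63 omits the frame test and Session 64 is undescribed, so the schedule does not deliver them.

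**2. Visit numbers.** As numbered, visits 34 and 35 are the Humphrey test and the 3-month follow-up frame test. Elsewhere the same section pairs visit 33 with visit 63, so the counterpart of 63 and 64 would be 33 and 34. That suggests a numbering slip for subjects who finish after one round.

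**3. The plan's own figure.** The Sample Size section gives a 95% half-width of 0.35 at n = 5 and 80% success: 1.96 × √(0.8 × 0.2 / 5) = 0.351. It reproduces. It concerns the success proportion and is not affected by this point.

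**4. How likely is a missing subject?** Inputs are 5 completers and success rate p = 0.80 (Sample Size). Assumption: a non-success is a subject with no VR improvement after two rounds.

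P(at least one) = 1 − p⁵

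| p | 1 − p⁵ |
|---|---|
| 0.90 | 1 − 0.590 = 41% |
| 0.80 | 1 − 0.328 = 67% |
| 0.70 | 1 − 0.168 = 83% |

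The expected number at p = 0.80 is 5 × 0.20 = 1.

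The protocol does not define success. If it means something stricter, such as reliable detection at 45°, some non-successes are partial improvers who do not fall under Session 63, and the figures drop. For example, if half of the 20% were partial improvers, 10% would show no improvement and the chance would be 41%.

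**5. How far would the mean change move?** Let four subjects change by d and the missing one by f × d.

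- Mean over all five: (4 + f)d / 5
- Mean over the four observed: d
- Ratio: 5 / (4 + f)

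f = 0 gives 5/4 = 1.25; f = 0.5 gives 5/4.5 = 1.11; f = 1 gives 1.00 (no bias). Both f values are assumptions.

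**6. Does the fix fit the visit?** The frame test is 5 trials × 5 azimuths × 2 sides + 5 blanks = 55 trials. At Session 35, allotted 1 hour, "The follow-up visit will consist of a peripheral visual field test, and NEI VFQ-25 and VA LV VFQ-48 questionnaires". Session 63 has the same hour and the same two questionnaires.

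**The case against.** The best reply is that the outcome section governs. It covers all participants and names visits 63 and 64, so field tests for repeaters are plainly intended and Session 63 is merely described incompletely. Figure 2, the timeline, is not shown in the text available here and might say so. This stands in part: the defect may be a conflict between two sections and not a deliberate choice. But staff follow the session descriptions, which are explicit, and a figure that said otherwise would only add to the conflict.

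Four stronger readings are tempting, and the documents do not support them.

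- *The condition on Session 33 removes the primary outcome from all non-responders.* The named after-treatment visits are 34 and 35, which carry no such condition. What excludes the two-round non-responder is the single last visit.
- *The response rate will be inflated.* VR progress data still identify non-response, so the count of responders need not change.
- *A biased mean change will carry into later trials.* The Sample Size section says that the findings will inform future designs, but the quantity it names is the response pattern and incidence, not the mean change.
- *There is a 67% chance of missing data as a property of the plan.* That figure depends on the assumed meaning of success and is an upper-end value at the 80% rate.

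It is also fair that the study is exploratory and small, which limits what any mean change will be taken to show.

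**Conclusion.** The point holds. As the text stands, a subject with no VR improvement after two rounds has no post-treatment Humphrey or frame-test result, contrary to a primary outcome set for all participants. The before/after ANOVA omits that subject because of outcome, and is biased toward benefit provided that the omitted subject gained less on the frame test than the others did.

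At the planned 80% rate the chance of at least one such subject among 5 completers is up to 67%. One missing subject in five overstates the mean change by up to 1.25-fold. These sizes rest on equating non-success with no VR improvement and on the assumed change in the missing subject. The conflict between the sections does not depend on either.

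**What to change.** 1. Add the existing peripheral frame test to Session 63 for every subject who completes a second round, whatever the VR result.
2. Describe Session 64 as the post-treatment Humphrey test for these same subjects, as the outcome section already implies.
3. Correct the visit numbers in Outcome Measure(s) so that the end-of-treatment frame test and Humphrey test are the primary after-treatment values: 33 and 34 after one round, 63 and 64 after two. Once Session 33 is named, its frame test should go to everyone who stops after one round, so that its VR condition does not open a new gap.
4. State in the Analytical Plan that all these subjects enter the before/after comparison.

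**Cost.** A protocol amendment; a few more minutes within the hour already allotted to Session 63, with the subject already on campus; and one optometrist visit of up to 1 hour per two-round non-responder. The mean change may look less favourable. The amendment should precede the first such subject's last visit, because an end-of-treatment field that was not measured cannot be recovered later.
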